5.5.1.2 Missing data imputation

For the purpose of missing data imputation, the following two scenarios will be considered:

- Jump to reference (J2R)
- Missing At Random (MAR)

The imputation will be based on all available data (i.e. from all scheduled time points) using all covariates as specified in the ANCOVA model. For J2R only placebo data will be used, for MAR data from the same treatment arm will be used for building the imputation model.

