- **Permanent discontinuation of study treatment due to AE, Lack of efficacy (LoE) and use of prohibited medication:** If retrieved drop-out data are available, these will be used for analysis. If no data was retrieved after study treatment discontinuation, missing data will be multiply imputed based on placebo arm data, i.e. “jump to reference” (J2R) assumption for the EMA401 arm, missing at random assumption for placebo arm ([Carpenter et al 2013](#)). More details on the imputation model will be specified in the statistical analysis plan prior to unblinding.
- **Permanent discontinuation of study treatment due to other reasons than AE, LoE and use of prohibited medication:** If efficacy data collected after study treatment discontinuation are available (retrieved drop-out), then the retrieved drop-out data will be excluded and missing data after study treatment discontinuation will be imputed via multiple imputation using the MAR assumption.

The multiple imputations for the primary efficacy variable (NRS) will be carried out on the weekly mean pain score.

The primary objective will be achieved if the EMA401 100 mg b.i.d. dose is statistically significant versus placebo in terms of the primary efficacy variable after multiplicity adjustment.

The key secondary objective will be achieved if the EMA401 100 mg b.i.d. dose is statistically significant versus placebo in terms of NPSI total score after multiplicity adjustment.

The primary population will be the FAS. To preserve the family-wise error rate at the 2.5% level when comparing the EMA401 100 mg b.i.d. dose versus placebo on the two endpoints NRS and NPSI, statistical testing will be carried out using the following sequentially rejective, weighted Bonferroni-type test using the graphical approach (Bretz et al 2009) mentioned in Figure 9-1.

Figure 9-1 **Sequentially rejective, weighted Bonferroni-type test using the graphical approach**

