These patients must continue to adhere to protocol requirements (see respective protocol Table 6-2). The design feature of retrieved drop-outs, considered in order to minimize the occurrence of missing data on primary pain parameter, is exploited for the statistical analysis as follows:

- **Permanent discontinuation of study treatment due to AE, lack of efficacy (LoE) and use of prohibited medication:** If retrieved drop-out data are available, these will be used for analysis. If no data was retrieved after study treatment discontinuation, missing data will be multiply imputed based on placebo arm data, i.e. “jump to reference” (J2R) assumption for the EMA401 arm, missing at random assumption for placebo arm (Carpenter, Roger, and Kenward 2013). Of note, alternatively one could build the imputation model based on the RDO data, however, we expect sparse RDO data which will likely hinder us to build an imputation model. More details on the imputation model are specified in Section 5.
- **Permanent discontinuation of study treatment due to other reasons than AE, LoE and use of prohibited medication (including discontinuation due to USM):** If efficacy data collected after study treatment discontinuation are available (retrieved drop-out), then the retrieved drop-out data will be excluded and missing data after study treatment discontinuation will be imputed via multiple imputation method using the MAR assumption.

The multiple imputations will be carried out on the weekly mean pain score. Details on multiple imputation can be found in Section 5 of this document.

The primary objective will be achieved if the EMA401 100 mg b.i.d. dose is statistically significant versus placebo in terms of the primary efficacy variable after multiplicity adjustment. To preserve the family-wise error rate at 2.5% level when comparing the EMA401 100 mg b.i.d. dose versus placebo on the primary and key secondary endpoints (see Section 2.6), statistical testing will be carried out using the following sequentially rejective, weighted Bonferroni-type test using the graphical approach (Bretz et al 2009) mentioned in Figure 2-1.

Figure 2-1 Sequentially rejective, weighted Bonferroni type test using the graphical approach

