2.5.3 Handling of missing values/censoring/discontinuations

Handling of missing daily pain score values within a week (within-week imputation)

The 24-hour average pain score is measured daily for seven consecutive days prior to randomization and then every day through the end of the study. At each week, the weekly mean of the seven 24-hour average pain assessments will be calculated.

The weekly mean will be calculated based on the available assessments. If only one measurement is available, the mean will be based on that value. Assessments made under treatment will not be mixed up with RDO data. If there is at least one value among the seven values in one week which is on-treatment, the mean will be calculated based on that.

Handling of missing weekly mean pain score values (weekly mean imputation)

The multiple imputation for the primary variable will be carried out on the weekly mean pain score.

The imputation procedure related to primary analysis is described in Section 2.5.2 while the imputation procedure for the supplementary analyses is included in Section 2.5.4. The details of these imputation rules are specified in the Estimand Charter and in Section 5.

For all analyses, imputation of intermittent missing observations before treatment discontinuation will be carried out following a MAR mechanism for all treatment arms.

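### The SAP's jump-to-reference rule, taken as written, gives copy-reference: a placebo-only model applied to EMA401 patients' own on-treatment scores

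*SAP*

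**What the plan says.** Protocol 9.4.2 and SAP 2.5.2 both name J2R for EMA401 patients who permanently stop for an adverse event, lack of efficacy or prohibited medication and have no data after the stop. Placebo patients in that position are imputed under MAR. The protocol leaves further detail of the imputation model to the SAP.

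SAP 2.5.2 passes the reader on: "More details on the imputation model are specified in Section 5". SAP 2.5.3 adds a second source: "The details of these imputation rules are specified in the Estimand Charter and in Section 5". Within Section 5, the only text on imputing missing scores is 5.5.1.2. It lists J2R and MAR as the two scenarios and gives two sentences. The second of them says which arm builds each model: "For J2R only placebo data will be used, for MAR data from the same treatment arm will be used for building the imputation model". The first sets the inputs for both scenarios alike: "The imputation will be based on all available data (i.e. from all scheduled time points) using all covariates as specified"; the covariates meant are those of the primary model.

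SAP 5.5 places the SAS code in the TFL shells. The NPSI analysis (SAP 2.6.2) and the responder analyses (SAP 2.7.1) take over the same handling of missing data.

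**The concern.** J2R treats the patient as an EMA401 patient up to the stop and as a placebo patient afterwards. It therefore needs the EMA401 arm means for the period before the stop. A model built from placebo data alone has no such means. If the patient's earlier weekly scores are predictors in it, any early benefit looks like an unusually good placebo patient, and the model predicts a good Week 12 score from it.

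That is copy-reference, a different estimator from the one named for the primary estimand, and it favours EMA401 whenever there is an early effect. It also departs from the meaning the protocol gives to J2R in its first supplementary analysis (9.4.4), where such a patient counts as no better than one on placebo. The amended SAP drops that analysis and the tipping-point analysis (SAP 4). The remaining supplementary analysis uses MAR after every stop (SAP 2.5.4.1), so no retained analysis would expose the difference.

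**Working it through.** **Inputs from the documents.** Effect 0.8 NRS points, SD 2.6 and 200 patients per arm (Protocol 9.8, SAP 3); 1:1 allocation; 137 patients randomised (SAP, Amendment 1); weekly mean scores as the imputed variable (SAP 2.5.2).

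**The plan's own figure.** With 200 per arm, 0.8 / (2.6 × √(2/200)) = 3.077. Power at one-sided 0.025 is Φ(3.077 − 1.960) = 86.8%, against about 85% stated. The agreement is close enough to use 0.8 and 2.6 below.

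**Assumed, because the documents do not give them.** Serial correlation, time course of the effect, timing of stops, the share of EMA401 patients imputed by J2R, a common covariance in both arms, and a 68/69 split. Central set: the effect rises linearly to its full size at Week 4 and stays there; last observed score at Week 2, 4, 6 or 8 in equal parts; exchangeable correlation 0.5 or 0.7, or AR(1) 0.9.

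**Formulas.** Let B be the regression of Week 12 on the scores from Week 0 to the last observed week.

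- J2R: imputed mean = μ(placebo, Week 12) + B × (own earlier scores − EMA401 earlier means)
- SAP rule as written: imputed mean = μ(placebo, Week 12) + B × (own earlier scores − placebo earlier means)
- Difference = B × (EMA401 earlier means − placebo earlier means)

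The difference is zero when there is no drug effect.

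**Share of the Week 12 effect retained (J2R retains 0).** Under exchangeable correlation ρ with n scores (baseline included), each score has weight ρ / (1 + (n − 1)ρ). Example with ρ = 0.5 and last score at Week 4: the weight is 0.5/3, the relative effects 0, 0.25, 0.5, 0.75 and 1 sum to 2.5, so the share is 0.417. Under AR(1) only the last score counts. Example at Week 4: 0.9⁸ × 1 = 0.430.

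| Correlation | Week 2 | Week 4 | Week 6 | Week 8 | Mean |
|---|---|---|---|---|---|
| Exchangeable 0.5 | 0.188 | 0.417 | 0.562 | 0.650 | 0.454 |
| Exchangeable 0.7 | 0.219 | 0.461 | 0.606 | 0.689 | 0.494 |
| AR(1) 0.9 | 0.174 | 0.430 | 0.531 | 0.656 | 0.448 |

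**Effect on the trial estimate.** J2R gives 0.8 × (1 − share imputed). The shift is mean retained share × 0.8 × share imputed.

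| EMA401 imputed (of about 68) | J2R | Shift | SAP rule as written |
|---|---|---|---|
| 5% (about 3) | 0.76 | 0.018–0.020 | 0.78 |
| 10% (about 7) | 0.72 | 0.036–0.039 | 0.76 |
| 15% (about 10) | 0.68 | 0.054–0.059 | 0.73–0.74 |

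**Against the standard error.** 2.6 × √(1/68 + 1/69) = 0.444 if all 137 count fully. If early stops leave 70% or 50% of that information (assumed), it is 0.444/√0.7 = 0.531 or 0.444/√0.5 = 0.628. The central shifts then run from 0.018/0.628 = 3% to 0.059/0.444 = 13% of one standard error.

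**Wider assumptions.** Exchangeable 0.3 to 0.85, AR(1) 0.7 to 0.95 and a plateau or linear effect, still with 5 to 15% imputed, give shifts of 0.002 to 0.075. That is not a bound: a full effect from Week 1, exchangeable 0.85 and 15% imputed gives 0.093, about 0.2 of a standard error.

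**Simulation check** (400,000 per arm, effect 0.8, a random 10% stopping after Week 6; the three correlations in table order):

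| Method | Estimated effect |
|---|---|
| J2R | 0.718 / 0.717 / 0.725 |
| Placebo-only model, baseline score alone | 0.718 / 0.718 / 0.724 |
| Placebo-only model, all earlier scores | 0.764 / 0.766 / 0.768 |

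With a true effect of 0 the three methods agree to within 0.001. Building on placebo data is therefore not the cause by itself. The excess comes from feeding EMA401 post-baseline scores into that model.

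**The case against.** The strongest reply is that copy-reference is only one reading. SAP 5.5.1.2 never says that earlier weekly scores are predictors. It refers to the ANCOVA covariates, and a placebo-only model with baseline covariates would match J2R on average, as the simulation shows. This reading is strained. The same two sentences also govern MAR imputation, which needs a patient's own earlier scores, and they call for data from all scheduled time points.

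Second, J2R is named repeatedly with a methodological reference, so a programmer who follows the named method would not produce copy-reference. It is also true that basing the imputation on placebo data in SAP 2.5.2 is consistent with J2R. That text contrasts placebo with retrieved drop-outs as the source for the period after the stop ("alternatively one could build the imputation model based on the RDO data"). But 5.5.1.2 is where the SAP sends the reader for the model, and its rule there does not produce the named method.

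Third, the Estimand Charter and TFL-shell code may settle the matter. This stands: nothing here shows what the program does.

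Fourth, the effect is small and rests on assumptions, the trial ended early, and stops due to the urgent safety measures go to MAR. This stands too and sets the severity.

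**Conclusion.** The concern holds as a minor fault in the SAP text. The stated rule omits how scores before the stop enter the J2R model and, taken as written, yields copy-reference. Under the central assumptions the estimate moves 0.02 to 0.06 NRS points in favour of EMA401 if the drug works early, and not at all if it does not, so no inflation of the false-positive rate is claimed. The size depends on the assumed correlation, time course, stop timing and imputed share. Only stops for an adverse event, lack of efficacy or prohibited medication without retrieved data are affected. Confidence is medium because the Charter and code were not available.

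**What to change.** Add one sentence to SAP 5.5.1.2: for J2R, an EMA401 patient's earlier scores enter as deviations from the EMA401 arm means up to discontinuation, and placebo means and covariance apply afterwards. State that the same holds for NPSI and the responder analyses. Check the Estimand Charter and the TFL-shell code against it before database lock. If copy-reference is what is wanted, name it and justify it against the primary estimand.

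The cost is one sentence, a document check and at most one change to the imputation program, with no burden on patients or data collection. The downside is that the estimate may be slightly less favourable to EMA401.

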5.5.2 Secondary analysis

5.5.2.1 Logistic regression

The proportion of responders will be analyzed using a repeated measures logistic regression. The model is similar to the ANCOVA model:

Response = intercept + treatment + sex + age + PDNmed (yes/no) + baseline (mean pain intensity) + error.

The SAS procedure GENMOD will be used.

Odds ratios will be presented along with 95% confidence intervals and p-values for the treatment contrasts.

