9.5 Analysis of secondary variables

9.5.1 Efficacy variables

The following secondary efficacy variables will be evaluated:

1. Responder analyses (based on at least a 30% or 50% improvement from baseline on NRS) will be performed in order to facilitate the interpretation of the results of the primary and supplementary analyses from a clinical relevance perspective. The responder status for each patient will be calculated based on the continuous weekly score measurements. For

patients who prematurely discontinue study treatment, the responder status will be calculated after missing data are imputed via multiple imputation according to the approaches specified for the primary and two supplementary analyses. Further analyses will be performed by considering patients who discontinue study treatment due to specific discontinuation reasons as non-responders. Additionally, to study the effect of changes in doses of concomitant medications for PDN, the use of prohibited medications and rescue medications on the responder criteria, a combined responder status of the patients will be calculated based on their continuous weekly score along with the use of the medications mentioned above. These analyses will be performed on the FAS population. The detail definition of the responder status and the corresponding secondary estimand and its supplementary estimands are defined in detail in an Estimand Charter.

From an analysis point of view, the resulting responder variables will be analyzed using a logistic regression model including all randomized patients and adjusting for the same covariates as the ANCOVA model for the primary analysis. Odds ratios will be estimated along with their 95% CIs.

The responder analyses will be performed for each visit, with the obvious modification in the definition for the week of interest.

2. Change from baseline to Week 12 in BPI-SF interference total score. This variable will be analyzed according to the same ANCOVA model as the one used for the primary variable.
3. Change from baseline to Week 12 in weekly mean of the 24-hour worst NRS pain score, using an 11-point Numeric Rating Scale (NRS). This variable will be analyzed according to the same ANCOVA model as the one used for the primary variable.
4. PGIC at Week 12. The proportional odds model with the same factors as the ANCOVA model for the primary variable will be used.
5. The temporal items of NPSI will be summarized descriptively.

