The primary analysis on the change from baseline to Week 12 in the weekly mean of the 24-hour average pain score will be performed as originally planned. Besides the primary estimand, which is of main clinical interest, the supplementary estimand, which provides insight into the magnitude of improvement in efficacy that might be achieved if all patients were able to take EMA401 as prescribed for 12 weeks, will be analysed. The other planned supplementary estimands will be dropped, as they are of minor interest in the situation with many study treatment discontinuations due to trial termination in the scope of the Urgent Safety Measures (USM).

To support the primary analysis and to get an idea about the effect that might be achieved if the trial had not been terminated and if all patients had the chance to complete the Week 12 assessment, a sensitivity analysis on a modified population will be performed. The modified full analysis set will include all patients who had a chance to complete the study before the termination date, i.e. who had been randomized at least 12 weeks before study termination date.

Similar considerations were made for the key-secondary endpoint.

Due to the considerably reduced number of patients who completed the study, only descriptive subgroup analyses will be provided. Moreover, the secondary endpoints will also be summarized descriptively only.

1 Introduction

This statistical analysis plan (SAP) describes all planned analyses for the Clinical Study Report (CSR) of study CEMA401A2202, a Phase 2, double-blind, placebo-controlled, randomized trial to determine the safety and efficacy of EMA401 in reducing 24-hour average pain intensity score in patients with painful diabetic neuropathy.

The content of this SAP is based on the final version of protocol CEMA401A2202 (release date 15-Sep-2017). All decisions regarding final analysis, as defined in the SAP document, have been made prior to database lock and unblinding of the study data.

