In the graphical testing procedure given in Figure 2-1, H1 and H2 denote the two null hypotheses of no treatment difference of EMA401 100 mg b.i.d. vs. placebo for the primary efficacy variable NRS and key secondary efficacy variable NPSI total score. The corresponding alternative hypotheses will be EMA401 100 mg b.i.d. is superior to placebo for the NRS and NPSI respectively. In the Figure 2-1 the number in the circle represents the proportion of alpha level to be assigned at the initial stage among the two null hypotheses. The direction and the number in the arrow represent the proportion of the alpha to be propagated to the next hypothesis. Initially, H1 will be tested at the full alpha level (1 sided) 0.025. If H1 is rejected then H2 will be tested also at the full alpha level (1 sided) 0.025.

To facilitate the interpretation of the estimated treatment difference a standardized effect size will be provided and will be calculated based on the results of the ANCOVA analysis.

The same ANCOVA model will be applied at the visits prior to Week 12. Multiplicity adjustment at visits prior to Week 12 will not be carried out.

Summary statistics for absolute values and change from baseline by treatment and visit will be provided for the original measurements (i.e. for the raw data prior to multiple imputation) of the primary efficacy variable. If a measurement is collected under the period of use of prohibited medications or the 7 days thereafter, it will be excluded from the summaries. ■

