2.7.1 Responder Analysis

Responder analyses (based on at least a 30%, 50% improvement from baseline on NRS) will be performed in order to facilitate the interpretation of the results of the primary and supplementary analysis from a clinical relevance perspective. These analyses will be performed on the FAS population. One secondary estimand is considered, together with one supplementary estimand.

The secondary estimand and the supplementary estimand to the secondary estimand differ from the primary and supplementary estimand in two ways:

- First, the variable of interest is the responder status in NRS score, with response status corresponding to at least a 30% (50%) improvement in pain from baseline.
- Second, the measure of intervention effect is the odds ratio of the proportions of responders between investigational drug and placebo.

The other features characterizing these responder analyses are exactly the same as for the primary and the t supplementary analysis, respectively.

From an analysis point of view, the responder status for each patient will be calculated on the continuous weekly score measurements after missing data are multiply imputed based on the approach specified corresponding to the primary analysis and the supplementary analyses. If the patient is a completer but week 12 measurement is affected by the changes in doses of concomitant medication for PDN or the use of prohibited medication then the responder criteria will be defined based on the multiply imputed values by MAR. The resulting responder variable will be analyzed using a logistic regression model including all randomized patients and adjusting for the same covariates as the ANCOVA model for the primary analysis.

From an analysis point of view, the resulting responder variables will be analyzed using a logistic regression model including all randomized patients (FAS population) and adjusting for the same covariates as the ANCOVA model for the primary analysis. Odds ratios will be estimated along with their 95% CIs.

The responder analyses will be performed for each visit, with the obvious modification in the definition for the week of interest.

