5.5 Statistical models

SAS codes for all statistical methodology described in this section will be included as programming note in TFL Shells.

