5.5.1 Primary analysis

5.5.1.1 ANCOVA

The primary analysis (and all other analyses of continuous variables) will be done using analysis of covariance. The model is:

mean pain score = intercept + treatment + sex + age + PDNmed (yes/no) + baseline (mean pain intensity) + error.

The SAS procedure MIXED will be used for computing p-values and 95% confidence intervals for LS means.

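### Does the repeated-measures label on the responder model in SAP 5.5.2.1 put the Week 12 odds ratio in doubt?

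*SAP*

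**What the plan says.** SAP 5.5.2.1 states: "The proportion of responders will be analyzed using a repeated measures logistic regression". The equation printed below it contains treatment, sex, age, use of PDN medication and baseline pain. It has no visit term, no treatment-by-visit term and no within-patient correlation structure. SAS GENMOD is named as the procedure. The output is described as follows: "Odds ratios will be presented along with 95% confidence intervals and p-values for the treatment contrasts".

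SAP 2.7.1 derives responder status from the multiply imputed weekly scores, fits a logistic regression with the ANCOVA covariates, and adds: "The responder analyses will be performed for each visit, with the obvious modification in the definition for the week of interest". Protocol 9.5.1 says the same: "the resulting responder variables will be analyzed using a logistic regression model including all randomized patients and adjusting for the same covariates". The endpoint table in SAP 1.2 places the responder objective at Week 12.

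The narrative headed Amendment 1 at the front of the SAP also says: "Moreover, the secondary endpoints will also be summarized descriptively only".

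**The concern.** One model over repeated observations and a separate model at each visit are different analyses, and the SAP names both for the same endpoint. The printed equation does not fully define a repeated-measures model. GENMOD can fit either kind, so the choice of procedure does not settle the matter. The code is outside the SAP: "SAS codes for all statistical methodology described in this section will be included as programming note in TFL Shells".

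A programmer who took the label and the equation at face value could stack all visits, fit a single treatment term and report the result as the Week 12 odds ratio. If the drug effect builds over time, that number would understate Week 12. If the effect fades, it would overstate it.

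The Amendment 1 sentence raises a second doubt: whether responders are modelled at all, or only described.

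**Working it through.** The documents give no planning figure for the responder analysis, so there is none to reproduce. The question is mainly one of reading.

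**1. Which model do the texts point to?**

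- The ANCOVA equation in SAP 5.5.1.1 reads "mean pain score = intercept + treatment + sex + age + PDNmed (yes/no) + baseline (mean pain intensity) + error". Its right-hand side is the same as that of the responder equation, and 5.5.2.1 describes the responder model as similar to it.
- The ANCOVA is fitted one visit at a time. SAP 2.5.2 says "The same ANCOVA model will be applied at the visits prior to Week 12". An equation without a visit term is therefore how this SAP writes a single-visit model.
- SAP 2.7.1 asks for an analysis at each visit and gives a rule for a completer whose Week 12 value is affected by a medication change. Both presuppose a visit-specific response.
- SAP section 4 lists the changes from the protocol. For the logistic regression it records only the removal of region. It declares no change of model type.
- Multiple imputation gives every patient a responder status at each week, so the usual reason for a repeated-measures model, using partly observed patients, does not arise.

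**2. What if a repeated-measures model was intended?** With treatment-by-visit terms it still yields a Week 12 odds ratio. In one simulated data set with treatment and visit as the only terms, it equalled the single-visit logistic result (1.70 and 1.70), while the fit without a visit term gave 1.49. With the other covariates held common across visits the two need not match exactly.

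**3. What would the stacked fit do?** Ignoring covariates, the stacked odds ratio is approximately [p̄₁/(1−p̄₁)] / [p̄₀/(1−p̄₀)], where p̄ is the response rate averaged over weeks.

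Take assumed rates over 12 weeks: placebo 0.10 + 0.20·w/12 and active 0.10 + 0.35·w/12. The mean of w/12 is 6.5/12 = 0.5417.

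- p̄₀ = 0.10 + 0.20 × 0.5417 = 0.2083 and p̄₁ = 0.10 + 0.35 × 0.5417 = 0.2896.
- Stacked: (0.2896/0.7104)/(0.2083/0.7917) = 1.55.
- Week 12: (0.45/0.55)/(0.30/0.70) = 1.91.

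With a constant odds ratio the two are 1.88 and 1.91. With an effect that peaks at Week 6 and is gone by Week 12, they are 1.50 and 1.00.

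A second calculation uses the trial's planning values where they exist: SD 2.6; placebo change −1.60 and difference 2.29 − 1.60 = 0.69 from the four-week study in post-herpetic neuralgia; and 0.8 assumed at Week 12. The following are assumed and not in the documents: baseline mean 6.5 and SD 1.3, SD 2.6 taken as the SD of change given baseline, a placebo change reached linearly by Week 4 and then flat, and every time course of the drug effect. For 30% response the Week 12 rates are 0.444 and 0.565, and the Week 12 odds ratio given baseline is 1.64.

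| Assumed drug effect | Stacked odds ratio, 12 weeks | Log shift |
|---|---|---|
| 0.8 throughout | 1.63 | −0.005 |
| 0.69 from Week 1, rising to 0.8 over Weeks 4–12 | 1.56 | −0.047 |
| As above, with a ramp from 0 over Weeks 0–4 | 1.49 | −0.097 |

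The standard error of the Week 12 log odds ratio with 137/2 = 68.5 patients per arm, all counted as observed, is √[1/(68.5 × 0.444 × 0.556) + 1/(68.5 × 0.565 × 0.435)] = √(0.0591 + 0.0594) = 0.344. The ramp shift is 0.097/0.344 = 28% of that. Stacking only the seven scheduled visits gives −0.121, or 35%. The largest shift over the ranges tried for SD, baseline mean and placebo change is −0.20, or 58%.

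**4. Modelled or descriptive?** The document history in the SAP names the endpoints that became descriptive: BPI-SF, PGIC, worst NRS and ISI. It lists responders separately, with only the supplementary analyses reduced. Section 4 follows the same split and amends the logistic regression by removing region, which makes sense only if that model is kept. Sections 2.7.1 (modelled) and 2.7.2 (descriptive) agree.

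**The case for a change.** The strongest case for a change is that the mismatch is on the page, the model type is not explained in section 4, the code cannot be seen, and deleting two words before database lock would cost almost nothing. The stacked fit is not harmless either. With a fading effect it could report an odds ratio of 1.50 where the Week 12 value is 1.00, so no general bound on the error can be claimed.

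Part of this stands. The label is ambiguous, and it would be tidier without the two words. But the harm needs a programmer to treat the printed equation as complete, stack the visits, set aside the per-visit instruction in SAP 2.7.1, and then label one pooled number as Week 12. That fit gives a single odds ratio and so cannot fill the per-visit results that 2.7.1 asks for. The gap would show up as soon as the tables were produced.

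The point about descriptive summaries does not stand. The Amendment 1 sentence is a loose summary of changes, and the specific sections settle the matter. The p-value that appears in 5.5.2.1 but not in 2.7.1 is additional output and contradicts nothing.

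**Conclusion.** No change to the plan is needed. The label in SAP 5.5.2.1 is most likely a clerical slip. The endpoint (Week 12), the effect measure (an odds ratio of responder proportions) and the per-visit fitting are all fixed elsewhere in the SAP and in the protocol. If the label is stray, its effect on the result is nil. If a true repeated-measures model with treatment-by-visit terms was meant, the Week 12 odds ratio is still reported and should be essentially the same.

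Only the stacked fit would alter the result. The shifts calculated for it rest on assumed time courses and on complete Week 12 data for all 137 patients, so they illustrate direction and are not estimates for this trial. Even then the damage would be confined to a secondary endpoint without multiplicity adjustment in an abbreviated report. The primary NRS and key secondary NPSI analyses do not depend on it.

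The conclusion rests on analysts reading 5.5.2.1 together with 2.7.1, which the SAP's structure makes the natural course. The programming notes in the table shells were not available to confirm it.
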